Hybrid Ablation Plus Medical Therapy for Persistent Atrial Fibrillation
(HYBRID-AF)

ClinicalTrials.gov ID: **NCT04190186**

March 03, 2025

Statistical Analysis Plan for the HYBRID-AF Trial

1. Introduction This Statistical Analysis Plan (SAP) outlines the planned statistical analyses for the HYBRID-AF Trial, which has concluded.

2. Study Objectives The HYBRID-AF Trial evaluates the effectiveness of Biotronik ICM-guided intervention in reducing atrial fibrillation (AF) burden in patients with symptomatic persistent AF post-ablation. The primary objective is to compare AF burden between months 3 and 15 post-ablation between the Biotronik ICM-guided arm and the conventional AF management arm.

3. Study Design

- Randomized, controlled trial with 90 subjects assigned 1:1 to either conventional AF management or Biotronik ICM-guided management.
- Follow-up assessments at 3, 6, 9, 12, and 15 months post-randomization.
- Primary and secondary endpoints will be analyzed according to the intent-to-treat (ITT) principle.

4. Endpoints

Primary Endpoint:

- AF burden, defined as the percentage of time a subject experiences AF between months 3 and 15 post-ablation, measured by the Biotronik ICM.

Secondary Endpoints:

1. Composite endpoint of:
 - Clinically significant (>30 min) atrial arrhythmia (AF, atrial flutter, or atrial tachycardia) detected by Biotronik ICM post-index ablation.
 - Symptomatic AF recurrence (any duration).
 - Repeat AF ablation.
 - Cardiac hospitalization.
 - Death.
 - Healthcare utilization (hospitalization, ED visits, unplanned office visits).
2. Incidence of atrial flutter or tachycardia post-ablation.
3. Incidence of repeat procedures.
4. Major adverse events requiring rehospitalization.
5. Quality of life (QOL) assessment.

5. Sample Size Justification Based on prior studies and preliminary data, AF burden is expected to be 25% in the conventional group and 16% in the intervention group, with a standard deviation of 15%. A Wilcoxon rank-sum test at a two-sided alpha level of 0.05 and 80% power determined that 90 subjects (with a 10% dropout rate) were required.

6. Statistical Methods

Primary Analysis:

- AF burden comparison between groups using the Wilcoxon rank-sum test.
- Descriptive statistics for median and interquartile range (IQR) of AF burden.
- Sensitivity analysis for missing data using multiple imputation.

Secondary Analyses:

- Kaplan-Meier survival analysis for time to first atrial arrhythmia event.

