- Cox proportional hazards regression for risk factors associated with AF recurrence.
- Poisson regression for healthcare utilization.
- Mixed-effects models for QOL changes over time.

Subgroup Analyses:

- Stratification by baseline AF burden, age, and sex.
- Sensitivity analysis excluding early dropout subjects.

7. Data Handling

- All analyses will follow an ITT approach.
- Missing data will be addressed using multiple imputation and sensitivity analyses.
- Data management will be conducted per Good Clinical Practice (GCP) guidelines.

8. Reporting and Interpretation

- All results will be reported with 95% confidence intervals and p-values.
- Statistical significance is defined as $p < 0.05$.
- Study findings will be presented in accordance with CONSORT guidelines.

9. Conclusion This SAP ensures rigorous and transparent statistical analyses for the HYBRID-AF Trial, aligning with ClinicalTrials.gov reporting requirements.

Hybrid Ablation Plus Medical Therapy for Persistent Atrial Fibrillation

Lead Principal Investigator: [name]

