4. STUDY DESIGN

This is a multi-site, randomized clinical trial of approximately 90 subjects with 45 subjects in each arm randomized (1:1) to conventional AF management vs. Biotronik ICM-guided AF management following ablation for persistent AF. The study subject population will include subjects with history of persistent atrial fibrillation (sustained AF episode lasting more than 7 days, but less than 1 year), according to current guideline indications for persistent AF ablation and ICM (Biotronik ICM) implantation. Clinical and functional data will be

captured related to: activity, heart rate, blood pressure, weight, quality of life status, and clinical events.

A total of 4 high-volume sites will be enrolling subjects for this study. Estimated enrollment will be 1-2 subjects per study site per month. Patients will be enrolled at the time of the AF ablation and will be followed for 15 months after a 3 month blanking period following AF ablation. The planned study startup period is 3 months with an enrollment period of 10 months, a follow-up period of 15 months, and 2 months for closeout and analysis for a total of 30 months (2.5 years).

The CDC is responsible for data management, analysis, and coordination of logistics. The enrolling sites will manage all subject recruitment activity and data collection per protocol as well as interact with the CDC and enrolling site study team regarding study operations. The CDC will be responsible for overall study management, data management, data reporting, and center communications for the study.

Primary Endpoint

The primary endpoint is atrial fibrillation (AF) burden between months 3 and 15 after the ablation procedure (to exclude the first 3 month blanking period) by the Biotronik ICM in the conventional AF management versus the of Biotronik ICM-guided AF management arm.

Secondary Endpoints

1. Composite end point of:

- clinically significant (>30 min) atrial arrhythmia (atrial fibrillation, atrial flutter or atrial tachycardia) as detected and documented by Biotronik ICM after the performance of the index AF ablation procedure (excluding the initial 3-month blanking period), or
- symptomatic AF recurrence (regardless of duration), or
- repeat AF ablation, or
- cardiac hospitalization, or
- death
- healthcare utilization, defined as hospitalization for any cause, ED visits, and unplanned office visits

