- In-clinic follow up visits as scheduled for subjects per standard of care and will occur at 3, 9, and 15 months. These visits will include a medical assessment and subjects will be questioned about clinical and unexpected medical (adverse) events.
- Phone follow-up visits will be conducted by the study team at 6 and 12 months as part of the study. The study team will perform a medical assessment, and ask questions about medication changes, along with clinical and unexpected medical (adverse) events as part of these follow-up phone calls.
- Chart reviews will be performed by the study team at each time point and include data about clinical history, medications, ablation procedure, device implantation, and follow-up data will be collected from the medical record.
- Quality of life questionnaire will be completed on paper by the patient at baseline and 15 months as part of the research study activities.
- ECGs performed as standard of care at Baseline, 3 month, 9 month, and 15 month.
- Endpoint assessment defined as AF burden, quality of life, and healthcare utilization (comprising the total of unplanned clinic visits, hospitalizations, repeat ablations, or death at 15 months.

Figure 2A: Management protocol for AF recurrence at Months 2 or 3 Post Ablation in the Intervention Arm*

[figure not shown]
[figure not shown]

Figure 2B: Management Protocol for AF Recurrence after 3 Post Ablation in the Intervention Arm

***If the patient is not on an AAD after the ablation, AAD will be initiated during the blanking period and continued post-blanking if there is ≥ 2 SCAF, 1 SCAF > 6 h or clinical recurrence. The type of AAD will left to the discretion of the treating physician as per standard of care. Repeat ablation can be offered if the patient does not tolerate or wish treatment with an AAD.**

Conventional AF Management Control Arm

- In the control arm, ICM data on SCAF recurrence will not be used to guide management. Management of clinical AF recurrence in the conventional management arm will be left to the discretion of the treating physician. The treating physician has access to all ICM data as standard of care and can use it per their discretion.
 - Management during the blanking period (ER): AAD management in the conventional arm, will be left to the discretion of the treating physician since

current guidelines do not provide specific recommendations (ref).

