Symptomatic AF recurrences during the blanking period will be treated with cardioversion and SCAF detected by the ICM will not drive management.

- Management after the blanking period (LR): If the patient was on medical therapy with an AAD, it will be discontinued after 3 months in the conventional arm, unless considered necessary by the treating physician. SCAF detected by the ICM will not drive management.
- Patients will attend scheduled in-clinic follow up visits at month 3, 9, and 15 as part of standard of care. These visits will include a medical assessment and questions about clinical and adverse events.
- Chart reviews will be performed by the study team at each time point and include data about clinical history, medications, ablation procedure device implantation, and follow-up data will be collected from medical record.
- Quality of life questionnaire complete on paper by the patient at baseline and 15 months as part of the research study activities.
- Phone follow-up visits will be conducted by the study team at 6 and 12 months. The study team will perform a medical assessment, and ask questions about medication changes, along with clinical and unexpected medical (adverse) events as part of these follow-up phone calls.
- ECGs performed as standard of care at Baseline, 3 months, 9 months, and 15 month.
- Endpoint assessment defined as AF burden, quality of life, unplanned clinic visits or hospitalizations, repeat ablation, death at 15 months.

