17. DATA ANALYSIS PLAN

For the primary endpoint of AF burden, i.e. percentage of overall follow-up spent by the subject experiencing atrial arrhythmias, the Wilcoxon rank-sum test will be used to statistically compare the conventional group vs. the active treatment group.

For the secondary composite end point, we will perform longitudinal event-free survival analysis, defined by survival and freedom from atrial arrhythmias, re-ablation, and cardiac hospitalization. Event-free survival rates, as captured by the composite secondary endpoint, will be displayed using the method of Kaplan-Meier. We will use the log-rank test to non-parametrically compare the overall survival curves for the two treatments. The other secondary endpoints of atrial flutter/tachycardia recurrence, repeat ablation incidence, and major adverse events will be compared utilizing negative binomial regression tests to statistically compare the event rates in the two arms, using the natural log of follow-up time as an offset. Quality of life measures will be compared between the arms using the non-parametric Wilcoxon rank-sum test.

The estimate for the sample size necessary to compare AF burden at 12 months between the conventional AF management arm vs. the Bio-Monitor 3-guided repeat ablation arm will assume a 1:1 distribution of subjects between the two arms. Since most of the re-ablation procedures will be carried out based on ICM-detected subclinical AF recurrences, we conservatively expect a re-ablation rate of 50% in the intervention arm vs. 5% in the conventional arm (in which only clinical episodes will be treated and resumption of antiarrhythmic medical therapy is also allowed).

For the planned analysis of the primary end point of AF burden involving the Wilcoxon rank-sum test, a two-sided $\alpha = 0.05$ and power of 80% was assumed. Based on our preliminary data and our prior studies on AF burden (The HARMONY Trial, Circulation Arrhythmia and Electrophysiology, 2015), the 12 month primary outcome of AF burden is assumed to be 25% vs. 16% in the conventional group, with a standard deviation of 15% (a conservative estimate which allows for 10% drop-out). A reduction from 25% to 16% and 80% power,

with a drop-out rate of 10%, will result in a total sample of 90 patients.

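### The SAP's Poisson model for healthcare utilization states no follow-up offset or overdispersion handling, and the items counted need to be reconciled

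*Combined protocol and SAP*

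**What the plan says.** **Model.** The whole entry in SAP Section 6 is "Poisson regression for healthcare utilization". SAP Sections 7 and 8 add no offset, dispersion check, robust variance or fallback. Section 7 names multiple imputation for missing data but does not say whether it covers visits after withdrawal.

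**Count.** The protocol's secondary endpoint list (Section 4) has "healthcare utilization, defined as hospitalization for any cause, ED visits, and unplanned office visits". SAP Section 4 names the same three kinds of contact, without saying any cause. The endpoint assessment bullet for the intervention arm in protocol Section 4 has instead "healthcare utilization (comprising the total of unplanned clinic visits, hospitalizations, repeat ablations, or death at 15 months". The matching bullet for the control arm reads "Endpoint assessment defined as AF burden, quality of life, unplanned clinic visits or hospitalizations, repeat ablation, death at 15 months" and forms no total.

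**Other event counts.** Protocol Section 17 says: "The other secondary endpoints of atrial flutter/tachycardia recurrence, repeat ablation incidence, and major adverse events will be compared utilizing negative binomial regression tests", and it does so "using the natural log of follow-up time as an offset". These are secondary endpoints 2 to 4. The SAP names no between-arm rate model for them. Its Kaplan-Meier line on first atrial arrhythmia touches endpoint 2 at most.

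**Follow-up.** Planned follow-up is 15 months. Protocol Section 13 uses data until withdrawal and keeps patients with under 3 months of follow-up in all secondary endpoints. Both documents assume 10% dropout.

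**The concern.** Plain Poisson regression sets the variance equal to the mean. Hospital and office visits often cluster in a few patients. If they do so here, the standard errors are too small, and a chance difference can be called significant under the SAP's p < 0.05 rule. Without an offset, a patient who leaves early counts as if observed throughout with few visits, so unequal dropout would bias the rate ratio.

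The items counted matter as well, because protocol Section 17 expects far more repeat ablations in one arm: "we conservatively expect a re-ablation rate of 50% in the intervention arm vs. 5% in the conventional arm". A total that adds ablations to visits would differ between arms for that reason alone.

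The outcome has some weight. Protocol Section 2 makes better resource utilization part of the hypothesis, and the SAP gives it its own regression. The SAP is dated March 2025 and says that the trial has concluded, so any choice it leaves open would be made after data collection.

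**Working it through.** The documents give no event rate, dispersion or power for this outcome, so there is no stated figure to reproduce.

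**Inputs from the documents:** 45 patients per arm, 10% dropout, nominal 5% significance, repeat ablation 50% vs 5%. **Assumed:** variance-to-mean ratio φ from 1 to 3; mean of 1, 1.5 or 2 visits per patient; dropouts leave on average halfway; the dropout splits in step 2.

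**1. Overdispersion.** If the variance is φ times the mean and the model assumes φ = 1, a two-sided test at nominal 5% has type I error 2[1 − Φ(1.96/√φ)]. For φ = 2, 1.96/1.414 = 1.386, which gives 0.166. Simulations with no true difference used 40 or 45 per arm, 10% dropout in both arms, a log follow-up offset, and 60,000 runs per setting.

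| φ | Formula | Simulated plain Poisson |
|---|---|---|
| 1 | 5.0% | 4.7–4.9% |
| 1.25 | 8.0% | 7.5–7.9% |
| 1.5 | 11.0% | 10.5–10.8% |
| 2 | 16.6% | 15.8–16.3% |
| 3 | 25.8% | 24.7–25.3% |

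With the variance scaled by the Pearson statistic and a t reference, the error was 4.8–5.3% in all of these settings. Repeat sets of runs stayed within 4.7–5.5%.

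**2. Offset.** With dropout proportion d, mean exposure is 1 − d/2 of full follow-up. Without an offset, the apparent rate ratio under no true difference is the ratio of mean exposures:

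- 10% vs 10%: 0.95/0.95 = 1.00
- 5% vs 15%: 0.975/0.925 = 1.05
- 0% vs 20%: 1.00/0.90 = 1.11

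In simulations with 45 per arm, mean 1.5 and φ = 1, Poisson type I error without the offset was 5.5%, 6.5% and 9.5% in these three cases, against 4.9–5.0% with it. At equal dropout the shift is under 1 percentage point.

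**3. Imputation against offset.** If a patient leaves at 7.5 of 15 months, and an imputed 15-month count is divided by the observed 7.5 months, that patient's rate is inflated by 15/7.5 = 2. Counts and exposure must cover the same period.

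**4. Items counted.** Set beside the endpoint lists, the intervention-arm bullet drops ED visits and adds repeat ablations and death. The effect of adding ablations alone, with equal visit rates m in both arms, is (m + 0.50)/(m + 0.05):

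- m = 1: 1.50/1.05 = 1.43
- m = 1.5: 2.00/1.55 = 1.29
- m = 2: 2.50/2.05 = 1.22

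There is no such shift if every repeat ablation is already counted once as a hospitalization, which the documents do not settle.

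**5. Endpoint 3 under the protocol's model.** If each patient has at most one repeat ablation, the count is 0 or 1, with variance p(1 − p) below its mean p. The negative binomial dispersion estimate then falls to zero. In simulations at 50% vs 5% it did so in every run (1,736 of 1,736 with 40 per arm; 1,798 of 1,798 with 45). Scaled Poisson intervals missed the true ratio in 4.8–5.2% of runs. The chance of no event in the 5% arm is 0.95^45 = 0.099, or 0.95^40 = 0.129 with 40 patients.

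**The case against.** The strongest reply is that the SAP is brief here rather than wrong. It does not forbid an offset or a scaled variance. At φ = 1 plain Poisson is sound, and the offset does little if dropout is balanced; the documents give only an overall 10%. The protocol assigns no regression model to healthcare utilization, so the Poisson line contradicts nothing. The outcome is also minor: in the numbered lists it is only one component of the secondary composite. All of this stands, and it makes the harm conditional. It does not remove the case for naming the model fully, since Section 17 already does so for the other counts.

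On the items counted, the SAP has one definition, and it matches the protocol's endpoint list. The other wording sits in an assessment bullet with an unclosed parenthesis, and the control-arm bullet lists similar items separately. A reader might infer that the plan prespecifies two rival counts. The text does not go that far; a misplaced bracket is a plausible explanation. A reader might also take the ratios of 1.43, 1.29 and 1.22 as the difference between the two definitions, or as evidence of false positives. They are neither: they leave out the loss of ED visits and the addition of deaths, and extra ablations would be real procedures.

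Finally, a reader might infer that the SAP has replaced the protocol's negative binomial model for endpoints 2 to 4. Neither document says so. The model in Section 17 stands, and the SAP merely fails to repeat it.

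**Conclusion.** The point holds as a specification gap with an inexpensive remedy. As written, the Poisson line leaves type I error dependent on a dispersion that the documents do not give: about 5% at φ = 1, rising to about 11%, 16% and 25% at φ = 1.5, 2 and 3. These are results over an assumed range. They do not show that the trial's counts are overdispersed, and a claim that the utilization test is in fact anti-conservative would go beyond the documents. The missing offset biases the rate ratio by about 5% at an assumed 5% vs 15% dropout and by about 11% at 0% vs 20%; with balanced dropout the effect is small. The mismatch in the items counted is real on the page but may be loose wording. It matters because of the expected imbalance in repeat ablation. The gap for endpoints 2 to 4 is minor. The primary Wilcoxon comparison is not affected.

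**What to change.** 1. **Model (SAP Section 6).** Replace plain Poisson with one named model that has log follow-up time as offset and handles dispersion: either Poisson with Pearson-scaled variance and a t reference, or the negative binomial model of protocol Section 17. Type I error was checked here only for the scaled Poisson. Apply the model to observed counts over observed follow-up, and state that full-period counts will not be imputed and then paired with an observed-time offset. Disclose that the model was specified after the trial concluded and that the SAP had named plain Poisson.
2. **Count.** Use the definition shared by the two endpoint lists, in both arms. State whether an admission for repeat ablation counts as a hospitalization, and reconcile the two assessment bullets in protocol Section 4. Repeat ablation and death are already separate components of the composite.
3. **Endpoints 2 to 4 (minor).** Cross-refer in the SAP to the negative binomial model of Section 17. For endpoint 3, name scaled Poisson with offset as the fallback when the dispersion estimate is zero or the fit fails; it is likely to be the model actually used. If an arm has no events, report counts with Fisher's exact test on patients with an event. Disclose that these fallbacks too were added after the trial concluded.

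**Cost.** A few lines of text and code. With the scaled Poisson, intervals are about 1.5% wider at φ = 1 because of the t reference, and about √φ times as wide under overdispersion: 1.1, 1.2, 1.4 and 1.7 times at φ = 1.25, 1.5, 2 and 3.

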For the primary outcome, no episode of AF occurring within the initial 3-month blanking period after ablation will be counted, although these will be tracked.

[figure not shown]
2. Incidence of atrial flutter or tachycardia after the index ablation procedure

3. Incidence of repeat procedures

4. Major adverse events requiring rehospitalization during follow-up

5. Quality of life (QOL) as assessed by Atrial Fibrillation Effect on QualiTy-of-life (AFEQT) questionnaire

Figure 1: Study Design

* Based on Biotronik ICM data after 1st Month

** Escalate to medical therapy or repeat AF Ablation based on current treatment (i.e. no treatment will be escalated to the AAD or repeat ablation, and if on AAD will be escalated to AF ablation).

*** Biotronik ICM data on subclinical AF will not be provided to the treating physician

As detailed in Figure 1 subjects who agree to participate in the study by signing the IRB-approved informed consent are randomized 1:1 into:

The Intervention ICM-based AF management Arm

- In the intervention arm, the ICM obtained data will be actively used to guide and monitor treatment (See Figure 2A and B). A report of AF data (comprising the total number of episodes, duration, average heart rate response, and correlation with patient-reported symptoms) will be provided to the treating physician/nurse at monthly intervals, starting from the first month post-AF ablation from the study team comprised of electrophysiologists and cardiologists. A general recommendation for early intervention with AAD continuation/resumption or redo AF ablation will be provided to the treating physician if recurrent AF episodes are detected by the ICM (≥ 2 episodes at a duration of ≥ 6 minutes each), even without the presence of clinical symptoms. However, the final decision regarding management will be left to the discretion of the treating physician.

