8. STUDY PROCEDURES

After signing the informed consent and undergoing ICM implant prior to or at time of the AF ablation as part of standard of care, subjects will undergo randomization and the following procedures:

12 lead ECG performed as standard of care.

- Quality of life (QOL) questionnaire will be completed by the patients as part of the research study on a paper form and entered into an electronic database by the research coordinator. The questionnaire should take the patient approximately ten minutes to complete.
- Chart Review: Data regarding clinical history, medications, ablation procedure, device implantation, and follow-up data will be collected from electronic medical records prior to in-clinic or follow up calls with the patients.
- In-Clinic Visits: Per standard of care, patients will attend scheduled follow up visits at 3, 9, and 15 months. The study team will perform a medical assessment, and ask questions about adverse events.

- Follow-Up Phone Calls: Patients will receive follow-up calls from the study team at 6 and 12 months. The study team will ask questions about medication changes and any unexpected medical (adverse) events as part of research.

Method of Assigning Subjects to Treatment

Subjects will be randomized 1:1 to conventional AF management vs. ICM-guided AF management following ablation for persistent AF. Randomization will occur electronically using the electronic data collection system, TrialMaster that is available 24/7 to all study personnel.

Follow-up Schedule (See also Figure 1 and Table 1)

Following enrollment and randomization to an intervention arm ICM-based AF management vs. conventional AF management, all subjects will have scheduled follow-up visits (clinic or phone) by the study team at quarterly intervals following randomization. ICM data will be collected electronically at monthly intervals.

All subjects will be followed for a time-period of 15 months.

The following data will be collected at these time-points:

Randomization/Baseline: Baseline clinical characteristics, existing echocardiographic measures, labs, QOL questionnaire, and NYHA class will be recorded.

- *Monthly:*
 - Conventional and Interventional arm
 - Obtain ICM data remotely
- *3-months ±14 days from randomization:*
 - Conventional
 - Office visit for clinical assessment
 - Clinical and adverse events
 - Discontinue AAD after 3 months following the AF ablation procedure per treating physician discretion
 - Interventional arm

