 - Office visit for clinical assessment
 - Clinical and adverse events
 - Decision on discontinuation of AAD after 3 months based on AF recurrences between 1-3 months detected by the ICM
- *6-months - 7 days/+21 days from randomization:*
 - Conventional
 - Phone follow up for medications
 - Clinical and adverse events
 - Resumption of AAD or repeat AF ablation based on clinical AF recurrence

- Interventional arm
 - Phone follow up for medications
 - Clinical and adverse events
 - Decision on resuming AAD or repeat AF ablation based on AF recurrences detected by the ICM.
- *9-months - 7 days/+21 days from randomization:*
 - Conventional
 - Office visit for clinical assessment
 - Clinical and adverse events
 - Resumption of AAD, repeat AF ablation, or no change in management based on clinical AF recurrence
 - Interventional arm
 - Office visit for clinical assessment
 - Clinical and adverse events
 - Decision on resume AAD or repeat AF ablation based on AF recurrences detected by the ICM.
- *12-months - 7 days/+21 days from randomization:*
 - Conventional
 - Phone follow up for medications
 - Clinical and adverse events
 - Resumption of AAD or repeat AF ablation based on clinical AF recurrence
 - Interventional arm
 - Phone follow up for medications
 - Clinical and adverse events
 - Decision on resume AAD or repeat AF ablation based on AF recurrences detected by the ICM
- *15-months - 7 days/+21 days from randomization:*
 - Conventional
 - Office visit for clinical assessment
 - Clinical and adverse events
 - Resumption of AAD or repeat AF ablation based on clinical AF recurrence
 - QOL questionnaire
 - Interventional arm
 - Phone follow up for medications
 - Clinical and adverse events
 - Decision on resume AAD or repeat AF ablation based on AF recurrences detected by the ICM
 - QOL questionnaire

Table 1: Data Collection Timepoints

	Screen/ Consent/ Random- ization	FOLLOW-UP					
Timeline		Monthly intervals after randomization	3 calendar months from randomization ± 14 days	6 calendar months from randomization - 7/+21 days	9 calendar months from randomization - 7/+21 days	12 calendar months from randomization - 7/+21 days	15 calendar months from randomization - 7/+21 days
Eligibility Confirmation/ Randomization	✓						
Demographics, PE, Medical Hx/NYHA	✓						
12 lead ECG (SOC)	✓		✓		✓		✓
Echocardiogram (SOC)	✓						
Labs (SOC)	✓						
Vitals (SOC)	✓			✓		✓	✓
CV Medication	✓		✓	✓	✓	✓	✓
Quality of Life	✓						✓
ICM Implant (SOC)	✓						

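### AFEQT quality of life has two unreconciled analyses, and neither commits to adjusting for the baseline score

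*Combined protocol and SAP*

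**What the plan says.** **Endpoint.** Protocol section 4 lists as the last of five secondary endpoints "Quality of life (QOL) as assessed by Atrial Fibrillation Effect on QualiTy-of-life (AFEQT) questionnaire". It does not say whether the variable is the 15-month score or the change from baseline.

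**Timing.** In both arms the form is completed twice. For the intervention arm, section 4 says "Quality of life questionnaire will be completed on paper by the patient at baseline and 15 months". The control-arm text and Table 1 agree.

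**Analysis.** Protocol section 17 says "Quality of life measures will be compared between the arms using the non-parametric Wilcoxon rank-sum test". SAP section 6 says "Mixed-effects models for QOL changes over time". The SAP line gives no fixed effects, covariance structure, baseline handling or contrast. Neither document says that its method replaces the other's. SAP section 8 promises 95% confidence intervals for all results, but the rank-sum line names no effect estimate to which an interval could attach.

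**Order of baseline form and allocation.** Section 8 says that, after consent and ICM implant, "subjects will undergo randomization and the following procedures"; the questionnaire is in the list that follows. The same section, under its combined randomisation and baseline entry, says "Baseline clinical characteristics, existing echocardiographic measures, labs, QOL questionnaire, and NYHA class will be recorded". Table 1 puts all of these steps in a single column. Section 4.1 places randomisation after the ablation and the ICM implant.

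**The concern.** With one score before and one after, the main design choice for a continuous outcome is how to use the first score. Here that choice is open. The two documents allow at least four analyses: a rank-sum test on 15-month scores, a rank-sum test on changes, a mixed model with a separate baseline mean for each arm, and a mixed model with a common baseline mean. They differ in precision and can give different answers. SAP section 1 says that the trial has concluded, so an open choice of method also leaves room to choose after the data exist.

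A second question is whether the baseline score can be trusted as a covariate. AFEQT is self-reported, no patient blinding is described, and nothing requires the form to be completed before the arm is known. If the arm coloured the baseline answers, every analysis that uses baseline would be biased.

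**Working it through.** **Inputs from the documents.** 90 subjects, 1:1, with 10% dropout (protocol section 17; SAP section 5), which leaves 81 evaluable, or 40.5 per arm. Two-sided alpha 0.05.

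**Not in the documents.** The AFEQT standard deviation, the target difference and the baseline-to-15-month correlation r. Results are therefore in SD units, with r assumed at 0.3, 0.5 and 0.7.

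**The plan's own figure.** There is none for quality of life. The total of 90 was set for AF burden: 2 × [15 × (1.960 + 0.842) / 9]² = 43.6, so 44 per arm or 88 in total before dropout, close to 90. It says nothing about AFEQT.

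**Step 1: relative variance of the arm difference** (equal SD at both times, linear relation, comparison of means).
- 15-month score only: 1
- Change score: 2(1 − r)
- ANCOVA: 1 − r²

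| r | 15-month only | Change | ANCOVA | 15-month ÷ ANCOVA | Change ÷ ANCOVA |
|---|---|---|---|---|---|
| 0.3 | 1 | 1.40 | 0.91 | 1.10 | 1.54 |
| 0.5 | 1 | 1.00 | 0.75 | 1.33 | 1.33 |
| 0.7 | 1 | 0.60 | 0.51 | 1.96 | 1.18 |

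ANCOVA beats the 15-month score at any non-zero r. Since 2(1 − r)/(1 − r²) = 2/(1 + r), it beats the change score at any r below 1. The change score is worse than the raw 15-month score when r < 0.5 and equal to it at 0.5.

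**Step 2: what this means with 81 subjects.** The standard error for 15-month scores is √(2/40.5) = 0.222 SD. The difference detectable with 80% power is 2.802 × 0.222 = 0.623 SD, multiplied by the square root of the relative variance for the other analyses.

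| r | Detectable: 15-month / change / ANCOVA (SD) | Power for an assumed 0.5 SD: 15-month / change / ANCOVA |
|---|---|---|
| 0.3 | 0.623 / 0.737 / 0.594 | 61% / 48% / 66% |
| 0.5 | 0.623 / 0.623 / 0.539 | 61% / 61% / 74% |
| 0.7 | 0.623 / 0.482 / 0.445 | 61% / 83% / 88% |

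For normal data the rank-sum test has relative efficiency 3/π, which moves the 15-month figure from 0.623 to 0.637 SD.

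**Step 3: where the SAP model falls.** A simulation with two raw scores per subject (40 per arm, 300 runs per setting) fitted a random-intercept model with a common baseline mean. At r = 0.3, 0.5 and 0.7 the spread of its arm estimate against that of ANCOVA was 0.206 against 0.207, 0.190 against 0.190, and 0.160 against 0.161. The two estimates correlated at 0.997 to 0.999. With a separate baseline mean for each arm, the arm-by-time term on complete data is essentially the change-score comparison. The SAP line fits either model.

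**Step 4: a contaminated baseline.** Assume no true effect and a 0.2 SD arm difference induced in the baseline answers. The expected bias is 0 for the 15-month score, −0.20 SD for change, and −0.20 × r = −0.06, −0.10 and −0.14 SD for ANCOVA. A simulation (40 per arm, 5,000 runs per setting) agreed with these. False rejection was about 5% for the 15-month rank-sum test, 11%, 14% and 20% for the rank-sum test on change, and 6%, 9% and 14% for ANCOVA.

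**The case against.** Four stronger readings are tempting, and the documents do not support them.

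- **The SAP model cannot be fitted.** A reader might infer that, with one change per subject, a random effect cannot be separated from residual error. That holds only if the change is the modelled outcome, which the SAP line does not settle. Two raw scores per subject identify a random intercept; in the Step 3 simulation the intercept variance came back as 0.30, 0.50 and 0.71. No loss of precision is shown for the SAP model as such.
- **The protocol test ignores baseline.** Section 17 is silent. A rank-sum test on changes would use baseline.
- **Baseline was taken after open-label randomisation.** The list in section 8 is not chronological, since it also contains chart review, clinic visits to 15 months and phone calls. Table 1 has one combined column, "Screen/ Consent/ Random- ization". The documents do not use the term open-label, and they do not say when a subject learns the arm. The most that the text supports is that the order is not fixed.
- **The questionnaire should be moved earlier.** The trial has concluded, so it cannot be.

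It is also fair to object that the two harms fall on different analyses. A 15-month-only test loses precision but is immune to a contaminated baseline, while ANCOVA gains precision and is exposed. And this is the last of five secondary endpoints, with no stated power.

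All of this stands. It narrows the point without removing it: two methods are named, neither is tied to a variable, and neither commits to baseline adjustment.

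**Conclusion.** The point holds as a gap in specification. One endpoint has two unreconciled analyses, and the baseline score that the trial collects is committed to neither.

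If 15-month scores alone are compared, the cost is a variance 10% to 96% larger than under ANCOVA for r from 0.3 to 0.7. If change scores or arm-specific baseline means are used, it is 18% to 54% larger over the same range. These figures rest on an assumed r, equal SDs at the two times and 81 evaluable subjects.

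Contamination of the baseline is a possibility that the text leaves open, not something that it shows. The 0.2 SD used above is an illustration. Because randomisation follows ablation, the baseline score may also be a post-ablation score. That does not bias the comparison of arms if the form preceded knowledge of the arm, but it changes what a change from baseline means.

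The effect is confined to a secondary endpoint and does not touch the AF burden analysis. The correction is still worth making, because it is cheap and uses data already in hand.

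**What to change.** 1. In SAP section 6 and protocol section 17, name one primary quality-of-life analysis: ANCOVA of the 15-month AFEQT score on arm and baseline AFEQT, reporting the adjusted mean difference with its 95% confidence interval. A two-time-point mixed model with a common baseline mean is an acceptable near-equivalent if it is written out in full. State whether the choice was made before AFEQT results by arm were seen.
2. Compare the date, and the time where recorded, of each baseline form with randomisation and ablation, and report how many forms came before each. The documents do not say what date or time the paper form carries, so some same-day cases may remain unresolved.
3. Add a sensitivity analysis of 15-month scores alone, which a contaminated baseline cannot bias, and read it beside the adjusted result.

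The cost is a few lines of wording, one check of existing records and one extra analysis. No new data are needed.
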